10.4 Data Monitoring

During the course of the study, safety and data quality monitoring will be performed on an ongoing basis by the Research Coordinator and the Principal Investigator. The clinical research coordinator will be responsible for collecting and recording all clinical data. This includes ensuring that all source documents exist for the data on the case report forms, ensuring all fields are completed appropriately, and all corrections are done according to Good Clinical Practice (GCP's). Any inconsistencies/deviations will be documented. The P.I. will review the obtained data for each patient on an ongoing basis.

10.5 Data Analyses

Descriptive statistics including the mean, standard deviation, median, and range will be used to summarize continuous variables. Frequency counts and percentages will be used to summarize categorical variables. Categorical variables, including 28 day mortality, will be compared between intervention groups using a chi-square test, or Fisher's exact tests if more appropriate. Continuous variables will be compared between intervention groups using an independent samples t-test, or Wilcoxon rank-sum test if more appropriate.

Logistic regression will be used to assess relationships between patient characteristics and binary study outcomes of interest. Continuous variables, including the time on cardiovascular support and time on ventilator, will be compared using t-tests or Wilcoxon rank-sum tests.

Time to event analyses will be conducted using Cox proportional hazards regression. For 28-day mortality, living patients will be censored after one month after the treatment was given. For overall survival, patients will be followed until time of death or date of last follow-up (maximum 6 months). Kaplan-Meier plots will be used to visually compare time to death from any cause between intervention arms followed by a log-rank test to compare survival distributions.

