Sample Size Justification	The rate of 28 day mortality from septic shock at the UT MD Anderson Cancer Center was 70% in 2017. With the objective of decreasing this rate to 40%, a sample size of 112 patients (56 per group) provides 90% power to detect a 30% absolute reduction in the rate of 28-day mortality using a two-sided chi-square test at the 0.05 significance level. We plan to use stratified randomization in a 1:1 fashion to assign patients into two groups, and a fixed block size consisting of 4

	patients will be used. The randomization will be conducted in CORe.
Brief Analysis Plan	
Descriptive statistics including the mean, standard deviation, median, and range will be used to summarize continuous variables. Frequency counts and percentages will be used to summarize categorical variables. Categorical variables, including 28-day mortality, will be compared between intervention groups using a chi-square test, or Fisher's exact tests if more appropriate. Continuous variables will be compared between intervention groups using an independent samples t-test, or Wilcoxon rank-sum test if more appropriate.
 
Logistic regression will be used to assess relationships between patient characteristics and binary study outcomes of interest. Continuous variables, including the time on cardiovascular support and time on ventilator, will be compared using t-tests or Wilcoxon rank-sum tests.
 
Time to event analyses will be conducted using Cox proportional hazards regression. For 28-day mortality, living patients will be censored at the end of 28 day follow-up after the treatment was given. For overall survival, patients will be followed until time of death or date of last follow-up (maximum 6 months). Kaplan-Meier plots will be used to visually compare time to death from any cause between intervention arms followed by a log-rank test to compare survival distributions.

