2.2 Epidemiology

Worldwide, 19 million cases of sepsis are calculated each year, however, it is presumed that this value may be even higher due to under reporting, which is considered high in low- and middle-income countries (3,4). According to the report of the Center for Disease Control and Prevention (CDC) of 2017, sepsis annually affects 1.5 million individuals in the United States, of whom 250,000 die (5), which includes it among the top 10 causes of death in the US. This generates annual costs of over 24 billion dollars(6); which makes this condition a public health priority.

In a recent study not yet published performed by [name] et al. in 2017, a sample of 305 patients (154 with hematologic malignancies and 108 with solid tumors) with the diagnosis of septic shock hospitalized in the ICU of The University of Texas MD Anderson Cancer Center were assessed. It was found that the 28 day mortality was 70%. These values shed light on the emergent requirement of seeking treatment alternatives that may improve outcomes in these patients.

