10.2 Sample Size Justification and Randomization

The rate of 28 day mortality from septic shock at the UT MD Anderson Cancer Center was 70% in 2017. With the objective of decreasing this rate to 40%, a sample size of 112 patients (56 per group) provides 90% power to detect a 30% absolute reduction in the rate of 28 day mortality using a two-sided chi-square test at the 0.05 significance level. We plan to use stratified randomization in a 1:1 fashion to assign patients into two groups, and a fixed block size consisting of 4 patients will be applied for this purpose. The randomization will be conducted in CORe (Figure 2).

Tables 3 displays effect sizes that correspond with conducting a test of equal proportions after randomizing 56 patients to each study arm. The first scenario in Table 3 is what we have currently provided in the protocol. Subsequent scenarios in Table 3 illustrate the change the in the effect size as the Type I error increases. Table 4 is provided to illustrate effect size results if the power is reduced to 80%. Smaller effect sizes are detectable if you increase Type I error or reduce power.

Table 3. Effect size with varying Type I error with Sample Size and Power controlled at 56 patients per study arm and 90%, respectively

Sample Size Per Study Group	Effect Size (percentage point change from $\hat{\pi}_0 = 70\%$)	Type I error
N = 56	-30% (0.70 vs 0.40)	0.05
N = 56	-27% (0.70 vs 0.43)	0.10
N = 56	-25% (0.70 vs 0.45)	0.15
N = 56	-24% (0.70 vs 0.46)	0.20

[figure not shown]
Estimates provided by (nQuery Advisor v7.0) for the difference between two proportions using a two-sided chi-square test.

Table 4. Effect size with varying Type I error with Sample Size and Power controlled at 56 patients per study arm and 80%, respectively

Sample Size Per Study Group	Effect Size (percentage point change from $\hat{\pi}_0 = 70\%$)	Type I error
N = 56	-26% (0.70 vs 0.44)	0.05
N = 56	-23% (0.70 vs 0.47)	0.10
N = 56	-21% (0.70 vs 0.49)	0.15
N = 56	-20% (0.70 vs 0.50)	0.20

Estimates provided by (nQuery Advisor v7.0) for the difference between two proportions using a two-sided chi-square test

Figure 2. Sample size and randomization

[figure not shown]

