The septic shock patients will be stratified by type of malignancy given that hematologic patients may be more morbid than solid tumor patients. SC + EMR: Early Metabolic Resuscitation plus Standard of Care SC: Standard of Care. Blue boxes represent the group of patients that will receive EMR plus Standard of Care intervention and the pink boxes represent the group that will receive Standard of Care alone.

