10.3 Interim Analysis

The parameters indicated in the full analysis set comprised of 112 patient for detecting an effect size of -30% (.70 vs .40) with a 2-sided test and Type I error of 5% conferring > 90% power were used to develop interim stopping boundaries based on the method of Lan-DeMets with an O'Brien Flemming type spending function. An interim analysis will be conducted when the first 56 patients (28 patients randomized per treatment arm) have been evaluated for the primary endpoint. Figure 1 provides the stopping boundaries for early termination on a p-value scale for both superiority and futility (East Version 6.3.1). At the interim analysis, a p-value < 0.003 or a p-value > 0.864 elicits early stopping for superiority or futility, respectively. The PI will make the final determination whether to terminate or continue with the trial after evaluating the study results. Accrual will not be suspended while this analysis is being conducted.

Figure 1. Stopping boundaries (on a P-value scale) for early termination due to superiority or futility

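### Randomization is stratified by malignancy type, but the primary chi-square and the log-rank test ignore the stratum; if the stratum is prognostic, the test is conservative and forgoes some power

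*Combined protocol and SAP*

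**What the plan says.** Section 10.2 sets the allocation: "We plan to use stratified randomization in a 1:1 fashion to assign patients into two groups", in fixed blocks of 4. The note to Figure 2 in that section gives the factor and a prognostic reason for it: "The septic shock patients will be stratified by type of malignancy given that hematologic patients may be more morbid than solid tumor patients".

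The analysis sections do not return to the factor. Section 10.5 states "Categorical variables, including 28 day mortality, will be compared between intervention groups using a chi-square test", with Fisher's exact test as the alternative, and the Brief Analysis Plan in the summary table says the same. For survival, Section 10.5 has Kaplan-Meier curves "followed by a log-rank test to compare survival distributions". Cox regression is named without covariates or strata. Logistic regression is offered for relating patient characteristics to binary outcomes, not as an adjusted comparison of the arms.

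Section 10.3 stops on a p-value scale: "a p-value < 0.003 or a p-value > 0.864 elicits early stopping for superiority or futility". It does not name the test that produces the p-value.

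**The concern.** When a prognostic factor is balanced by design, differences between strata no longer contribute to the chance imbalance between arms. The ordinary chi-square still counts that variation in its variance, so the test statistic is too small on average and the true type I error falls below 5%. An analysis that conditions on the stratum removes the excess variance and recovers the lost power.

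The stake is efficiency, not validity. The sponsor expects the factor to matter, records it for every patient at randomization, and then leaves it out of the main comparison. With 56 patients per arm and a sample size built on a 30-point reduction, there is little margin if the true effect is smaller.

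**Working it through.** **The plan's own figure.** Inputs from Section 10.2: 70% versus 40%, two-sided 0.05, 90% power, chi-square. With the pooled rate 0.55,

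n = [1.96·√(2·0.55·0.45) + 1.2816·√(0.70·0.30 + 0.40·0.60)]² / 0.30² = 55.7, so 56 per arm. Power at 56 is 90.2%. The stated design reproduces.

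**Inputs for the check.**
- Stratum mix: Section 2.2 reports "154 with hematologic malignancies and 108 with solid tumors". The hematologic share is 154/262 = 0.588, or about 33 hematologic and 23 solid-tumor patients per arm (w = 33/56 = 0.589). This is an assumption: 305 − 262 = 43 patients in that sample are in neither group.
- Overall standard-care mortality: 70% (Section 10.2).
- Gap d in standard-care mortality between strata: not in the documents, so varied from 0 to 40 points.
- Stratum rates: hematologic 0.70 + (1 − w)d, solid 0.70 − w·d. For d = 10, 20, 30 and 40 points this gives 74.1/64.1, 78.2/58.2, 82.3/52.3 and 86.4/46.4%.
- Treatment effect: a common odds ratio in both strata, solved so that overall mortality on SC + EMR is 40% (or 50%).
- Arms exactly balanced within strata, which blocks of 4 approximate.

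**Why the test is conservative.** With no treatment effect, the chi-square uses variance V = 0.70·0.30 = 0.21 per patient. The balanced design has V − w(1 − w)d². For d = 0.20: w(1 − w)d² = 0.2420·0.04 = 0.0097, leaving 0.2003. The true size is about 2·[1 − Φ(1.96·√(0.21/0.2003))] = 2·[1 − Φ(2.007)] = 4.5%.

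**Final analysis.** Exact enumeration of all outcomes, two independent binomials per stratum. Pearson z is without continuity correction, CMH z uses the hypergeometric variance, and both are compared with 1.96. Entries are chi-square / CMH, in percent.

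| Gap d (points) | Type I error | Power, 70 vs 40 | Power, 70 vs 50 |
|---|---|---|---|
| 0 | 5.1 / 5.0 | 89.6 / 89.6 | 57.6 / 57.2 |
| 10 | 5.0 / 5.0 | 89.7 / 89.9 | 57.6 / 58.0 |
| 20 | 4.6 / 5.0 | 90.1 / 91.1 | 57.7 / 60.4 |
| 30 | 3.9 / 5.0 | 90.8 / 93.1 | 57.8 / 63.7 |
| 40 | 3.1 / 5.0 | 91.7 / 95.1 | 58.0 / 67.8 |

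From unrounded values, CMH gains about 0, 0.2, 1.0, 2.3 and 3.3 points at 70% versus 40%. At 70% versus 50% it loses 0.3 points with no gap and gains 0.4, 2.8, 5.9 and 9.8 points otherwise.

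**Sensitivity to the mix.** With equal strata (28/28 per arm), the chi-square type I error is 5.1, 5.0, 4.6, 3.9 and 3.0%. At 70% versus 40% and a 20-point gap, power is 90.2 / 91.2%.

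**Interim.** 28 per arm (Section 10.3), taken as 16/12 by stratum, true rates 70% versus 40%, crossing at two-sided p < 0.003. The chance of crossing, chi-square / CMH, is 22.5/21.6, 22.4/22.4, 21.9/24.3, 21.0/26.7 and 19.8/30.0% for the five gaps. The two tests disagree on crossing in about 2, 2, 3, 6 and 10% of trials.

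The log-rank test was not simulated. The same variance argument applies to it.

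**The case against.** The strongest reply is that nothing the plan claims fails. Section 10.2 sizes the trial for a chi-square test and Section 10.5 analyzes with one; the test is valid and has about 90% power at the design effect in every scenario. Stratification still does the job stated for it, which is balance between the arms. On this view CMH is merely a more efficient option. That is right as far as it goes, and it is why the point is minor.

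Second, the gap between strata is unknown. The plan says only that hematologic patients may do worse. Up to 20 points, the loss at the planned effect is at most about 1 point. Losses of 2 to 3 points need standard-care mortality of 82% versus 52%, or 86% versus 46%, which nothing in the documents supports. This stands: the table shows a range, not an estimate. The 9.8-point figure also needs a true effect smaller than the one the trial is powered for, and even there CMH reaches only 67.8%.

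Third, the natural reading of Section 10.3 is that the interim p-value comes from the chi-square test used for sizing. This also stands. The disagreement rates therefore show what a change of test would do at the interim; they do not show a contradiction in the plan. They do mean that the statistic should be fixed before interim data are seen, since the trial is unblinded and the principal investigator makes the stopping decision.

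Finally, malignancy type could enter the Cox or logistic models. Neither is specified that way for the comparison of arms, so this softens the omission without filling it.

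**Conclusion.** The concern holds and is minor. The design stratifies on a factor the sponsor thinks prognostic, and no specified comparison of the arms uses it. The consequence is a conservative test, not a biased one: type I error is at or below its nominal level apart from the usual discreteness (5.1% with no gap), and the sample size is not undermined.

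At the planned effect the power forgone is about 0 to 1 point for gaps up to 20 points and 2 to 3 points for gaps of 30 to 40. It becomes substantial only if the strata differ by 20 points or more and the true effect is below 30 points; at 70% versus 50% the trial is underpowered under either test. These sizes rest on the assumed gap, the mix from Section 2.2, a common odds ratio and exact balance within strata. The final-analysis figures make no allowance for the interim look or for dropout. The omission itself, and the direction of its effect, do not depend on those assumptions.

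**What to change.** - In Section 10.5 and the Brief Analysis Plan, make the primary test of 28-day mortality a Cochran-Mantel-Haenszel test stratified by the randomization stratum.
- In Section 10.3, state that the same statistic supplies the interim p-value.
- Use a stratified log-rank test, and state that the Cox model is stratified by malignancy type.
- Keep the unstratified chi-square and log-rank tests as sensitivity analyses.
- Name the stratum levels in the text of Section 10.5, including where a patient in neither listed group belongs. Figure 2 may already show the levels; it could not be read here.

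The cost is wording only: the stratum is already recorded at randomization and the sample size does not change. If the strata turn out not to differ, CMH gives up essentially nothing at 70% versus 40%, about 0.3 points of power at 70% versus 50%, and about 0.9 points of interim crossing probability (22.5% − 21.6%).

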5.0 SELECTION AND ENROLLMENT OF PARTICIPANTS

5.1 Inclusion Criteria

- Adult patients aged 18 years old or older
- Admitted to the adult medical intensive care unit (MICU)
- Diagnosis of Septic Shock within 12 hours of ICU admission , unless the patient is already admitted to the ICU, defined as meeting criteria for sepsis in addition to the following:
 - Vasopressor therapy needed to elevate MAP \geq 65 mmHg.
 - Lactate $>$ 1 mmol/L (9 mg/dL) and/or Base excess $<$ -2 after adequate fluid resuscitation.
- Sequential Organ Failure Assessment (SOFA) score meeting the following requirements
 - Cardiovascular SOFA \geq 2
 - Total SOFA score \leq 12
- Patients meeting the mentioned inclusion criteria and not able to tolerate enteral nutrition above 70% of their estimated daily caloric need

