7.0 STUDY PROCEDURES

7.1 Data to be collected prior to start of intervention

1. Patient demographics at time of ICU admission (age, gender, weight, height, BMI, race, ethnicity, date of birth)
2. Past medical and surgical history as recorded in the latest admission on the electronic patient record (EPR)
3. Date and reason for hospital admission, and source of admission.
4. Date, time and reason for ICU admission including any concomitant problems
5. Date and time of septic shock onset (start time defined by criteria for septic shock, vital information that should be carefully determined, since “Timely delivery of EMR before Mitochondrial Respiration slows down” is the crux of the study)
6. Suspected source of sepsis
7. Presence or absence of oncologic disease, state and diagnosis of metastatic disease at time of ICU admission if known
8. Nutritional status based on the assessment by the dietitian in the ICU (this may be recorded after onset of intervention if not available initially) including any history of weight loss or signs of malnutrition
9. Patient vital signs and hemodynamic status

10. Supplementary oxygen and NIV/intubation status
11. Baseline CBC, blood chemistry panel, coagulation screen and ABG (baseline defined as within 12 hours of randomization for venous tests and 4 hours for ABG – if these have not been done we will send additional baseline investigations)
12. Any relevant microbiology results (blood, urine cultures, wound cultures, serum microbiological tests) and pertinent imaging results (radiology reports only – images not to be recorded)
13. Admission Sequential Organ Failure Assessment (SOFA) score
14. Pregnancy status - women of child bearing potential (defined as women <60 who have not been postmenopausal for at least one year or have not had a hysterectomy) will have either a serum or urine B-HCG test to exclude pregnancy. A positive pregnancy test is grounds for exclusion from the study. This will have already been undertaken as a part of screening if the above criteria are met.

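### The primary 28-day mortality test leaves out baseline SOFA and the malignancy stratum, giving up some power and robustness to chance imbalance; the planned test is nonetheless valid

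*Combined protocol and SAP*

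**What the plan says.** Section 10.5 (and the Summary's analysis plan) names one between-arm test for the primary endpoint: "Categorical variables, including 28 day mortality, will be compared between intervention groups using a chi-square test", with Fisher's exact test as the alternative. Section 10.2 sizes the trial on the same test: "The rate of 28 day mortality from septic shock at the UT MD Anderson Cancer Center was 70% in 2017", and "a sample size of 112 patients (56 per group) provides 90% power to detect a 30% absolute reduction in the rate".

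Regression appears in 10.5 for another purpose: "Logistic regression will be used to assess relationships between patient characteristics and binary study outcomes of interest". No covariates are listed and the treatment effect is not mentioned. The Cox model in 10.5 also names no covariates.

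Severity and stratum data are available:
- Sections 5.1 and 5.2 admit only patients with total SOFA of 12 or less, so a score must exist at eligibility.
- Section 7.1 item 13 lists "Admission Sequential Organ Failure Assessment (SOFA) score" among data collected before the intervention. Section 7.2 adds daily SOFA, with day 0 the day of recruitment.
- Sections 4.0 and 10.2 stratify randomisation by type of malignancy only, on the ground that haematologic patients may be sicker.

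**The concern.** With 56 patients per arm, baseline severity can differ between arms by chance, and an unadjusted test leaves that variation in the comparison. SOFA is not a stratification factor, so neither design nor analysis deals with it. Malignancy type is dealt with in the design but then dropped from the analysis.

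Two things are at stake. The first is power, especially if the true effect is smaller than the 30-point reduction assumed. The second is credibility: in an un-blinded, single-centre trial, an adjustment chosen after an imbalance has been seen would persuade few readers, so it has to be prespecified.

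The choice of score also needs care. Section 5.1 sets a 12-hour window from ICU admission "unless the patient is already admitted to the ICU". For a patient who develops shock later in an ICU stay, the admission SOFA may predate the shock.

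**Working it through.** **1. Reproduce the plan's figure.** Inputs from 10.2: 0.70 versus 0.40, 56 per arm, two-sided 0.05, chi-square.

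Power = Φ[(|p0 − p1| − 1.96·√(2·p̄(1−p̄)/n)) / √((p0(1−p0) + p1(1−p1))/n)], with p̄ = 0.55.

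- Standard error under the null: √(2 × 0.55 × 0.45 / 56) = 0.0940
- Standard error under the alternative: √((0.21 + 0.24) / 56) = 0.0896
- Power = Φ[(0.30 − 1.96 × 0.0940) / 0.0896] = Φ(1.29) = 0.902

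Solving for 90% power gives 56 per arm, so the stated figure holds. The same formula gives 0.802 at 70% versus 44% (the 80%-power case tabulated in 10.2) and 0.581 at 70% versus 50%.

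**2. Power with SOFA in the model.** The strength of the SOFA–mortality association is an assumption, shown as a range that includes weak values because entry is capped at 12. Simulation: 20,000 trials per scenario, 56 per arm; SOFA discrete from 2 to 12 (assumed mean 8.2, SD 2.3); logit risk = arm intercept + b × standardised SOFA, with intercepts set so that each arm keeps its design mortality. The comparison is the uncorrected chi-square against the logistic likelihood-ratio test of arm adjusted for SOFA.

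| Odds ratio per SD (AUC) | 70% v 40%: chi-square → adjusted | 70% v 44% | 70% v 50% |
|---|---|---|---|
| 1.35 (0.58) | 89.5 → 90.7% | 78.6 → 80.5% | 57.7 → 59.9% |
| 1.65 (0.64) | 89.8 → 92.0% | 79.4 → 82.6% | 57.6 → 61.2% |
| 2.01 (0.69) | 89.8 → 92.9% | 79.7 → 84.8% | 57.7 → 63.6% |
| 2.72 (0.75) | 88.9 → 94.5% | 79.0 → 86.8% | 58.4 → 67.9% |

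Monte Carlo standard error is about 0.2 points near 90% (√(0.9 × 0.1 / 20,000) = 0.0021) and 0.35 points near 58%. To match the adjusted powers in the second column, an unadjusted test would need about 58, 60, 63 and 67 per arm. With no association at all, the two tests gave 89.6% and 89.9%, so adjusting for a useless score costs nothing visible.

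A second simulation, with a continuous severity score and a standardised risk difference, gave about 93%, 94% and 96% at AUC 0.66, 0.71 and 0.76 (70% v 40%), and about 63%, 65% and 69% at 70% v 50%. It supplies the upper end of the range.

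**3. Chance imbalance.** The difference in mean SOFA, in SD units, has standard error √(2/56) = 0.189. The chance that it is at least 0.3 SD is 2[1 − Φ(0.3/0.189)] = 11%. At the interim, with 28 per arm, √(2/28) = 0.267 gives 26%.

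In null trials (70% in both arms) with an imbalance that large, the chi-square rejected in 5.9%, 7.3%, 9.0% and 10.3% across the four rows above; the adjusted test rejected in 5.2–5.8%.

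**4. Overall type I error at 70% v 70%.** Exact enumeration puts the chi-square at 5.1%. The adjusted likelihood-ratio test ran at about 5.1–5.5%, and the standardised risk difference with a robust standard error at about 5.5–6%.

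**5. Which SOFA score.** Section 5.3 item C requires recruitment and start of study solution within 12 hours of both shock onset and MICU admission. Read alone, it makes the admission score at most about 12 hours old at the start of treatment. Section 5.1 relaxes the window for patients already in the ICU, and then the score could be much older. The day-0 score in 7.2 is close in time but is not stated to precede treatment.

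**The case against.** The strongest reply is that nothing is broken. The trial is sized on the test it plans to use, the power is as stated, and randomisation holds the overall type I error near 5%. Chance imbalance is already counted in that 5%. The unadjusted risk difference is simple and targets the 70% versus 40% contrast directly. All of this stands.

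A reader might infer from step 3 that the chi-square has an inflated error rate. It does not: the raised rates apply only to the minority of trials with a marked imbalance, and they average out to about 5% over all trials. A reader might equally infer that the chi-square is conservative, so that adjustment has no cost in type I error. That fails too: its exact size at the protocol's control rate is 5.1%, and the standardised estimator runs slightly above nominal, so a small part of that estimator's apparent gain is size.

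The gain also rests on an association that the documents do not give. If SOFA is weakly prognostic within its capped range, adjustment adds only 1 to 2 points at the design effect.

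Finally, a reader might conclude that the admission score is stale for everyone enrolled from within the ICU, or that a new SOFA assessment is needed. The 12-hour rule in 5.3 and the daily SOFA in 7.2 do not support that. A suitable score should already exist from the eligibility check; it only has to be named.

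**Conclusion.** The point holds as one of efficiency and robustness. It is an improvement worth making, not a correction of an error: the primary analysis is valid and 90% power is right on the protocol's inputs.

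Over an assumed AUC of about 0.58 to 0.76, adjusting for SOFA adds roughly 1 to 6 points of power at 70% versus 40% (to about 91–96%) and about 2 to 10 points or slightly more at 70% versus 50% (from about 57–58% to about 59–69%). Direction is secure; size is not, because it depends wholly on the assumed association.

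Not quantified here: the added effect of the malignancy stratum (no mortality by malignancy type is given), and the behaviour of the adjusted test at the interim thresholds with 28 per arm.

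**What to change.** In 10.5 and the Summary, prespecify as primary a logistic regression of 28-day death on arm, baseline total SOFA (continuous) and malignancy stratum as randomised.

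- Take the p-value from the likelihood-ratio test. Report the effect as a standardised (marginal) risk difference with a robust standard error, so the target stays the 70% versus 40% contrast. State that the likelihood-ratio test governs if the two disagree at the margin.
- Keep the chi-square as a supporting analysis and leave the sample size at 112.
- In 10.3, apply the p-value boundaries (0.003 and 0.864) to the same adjusted test, after checking its size by simulation at 28 per arm.
- In 7.1 item 13, define baseline SOFA as the last total score before randomisation, that is, the score used for eligibility. Add a rule for a missing score.
- Reconcile 5.1 with 5.3 on patients already in the ICU when shock begins.

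Cost: plan wording, and recording a score that eligibility already requires. The primary analysis becomes slightly less simple. The standardised risk difference with a robust standard error can run at about 5.5–6% type I error at this sample size, which is why the p-value should come from the likelihood-ratio test (about 5.1–5.5%).
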